5.2.6 Prohibited Medications

Medications that inhibit CYP3A4 may result in increased plasma pazopanib concentrations; therefore, co-administration of strong CYP3A4 inhibitors is **PROHIBITED** beginning 14 days prior to the first dose of study drug until discontinuation from the study. **Strong CYP3A4 inhibitors include (but are not limited to):**

- Antibiotics: clarithromycin, telithromycin, troleandomycin
- HIV: protease inhibitors (ritonavir, indinavir, saquinavir, nelfinavir, lopinavir)
- Antifungals: itraconazole, ketoconazole, voriconazole
- Antidepressants: nefazodone

5.3 Women of Childbearing Potential

Women of childbearing potential (defined as women with regular menses, women with amenorrhea, women with irregular cycles, women using a contraceptive method that precludes withdrawal bleeding, and women who have had a tubal ligation) are required to have a negative serum pregnancy test within 14 days prior to the first dose of pazopanib.

Female and male patients (along with their female partners) are required to use two forms of acceptable contraception, including one barrier method, during participation in the study and for 28 days following the last dose of pazopanib.

If a patient is suspected to be pregnant, pazopanib should be immediately discontinued. In addition a positive urine test must be confirmed by a serum pregnancy test. If it is confirmed that the patient is not pregnant, the patient may resume dosing.

If a female patient or female partner of a male patient becomes pregnant during therapy

or within 28 days after the last dose of pazopanib, the investigator must be notified in order to facilitate outcome follow-up.

5.4 Duration of Therapy

If at any time the constraints of this protocol are considered to be detrimental to the patient's health and/or the patient no longer wishes to continue protocol therapy, the protocol therapy should be discontinued and the reason(s) for discontinuation documented in the case report forms.

In the absence of treatment delays due to adverse events, treatment may continue indefinitely until one of the following criteria applies:

- Documented and confirmed disease progression
- Death
- Adverse event(s) that, in the judgment of the investigator, may cause severe or permanent harm or which rule out continuation of study drug
- General or specific changes in the patient's condition render the patient unacceptable for further treatment in the judgment of the investigator
- Suspected pregnancy
- Serious non-compliance with the study protocol
- Lost to follow-up
- Patient withdraws consent
- Investigator removes the patient from study
- The Siteman Cancer Center decides to close the study

Patients who prematurely discontinue treatment for any reason other than withdrawal of consent will be followed as indicated in the study calendar.

5.5 Duration of Follow-up

Patients will be followed every 2 months until death. Patients removed from study for unacceptable adverse events will be followed until resolution or stabilization of the adverse event.

6.0 DOSE DELAYS/DOSE MODIFICATIONS

As a general rule, if dose reduction of pazopanib is necessary, the dose should be reduced stepwise by 200 mg at each step, and the subject should be monitored for approximately 10 to 14 days at each dose level. If toxicity does not abate during this monitoring time, the pazopanib may need to be interrupted and/or the dose further decreased with continued monitoring for an additional 10-14 days at each dose level, and so on.

If the toxicity has abated with reduction of the dose and dose re-escalation is considered safe by the investigator, the pazopanib dose can then be increased step-wise back to the pre-event dose

(in 200 mg increments, after monitoring for 10-14 days at each dose level to ensure that toxicity did not recur or worsen).

Dose-level	0	-1	-2	-3	-4
Dose	800 mg QD	600 mg QD	400 mg QD	200 mg QD	Discontinue

For patients at dose-level -3, 200 mg QD, a maximum dose delay of 14 days is allowed for management of toxicities. If toxicity does not resolve in 14 days, the patient should be discontinued from study.

Dose Modification Algorithms for Potential Treatment-Related Adverse Events

AE Terms & Descriptions	Dose Modification Algorithms
Hypertension	
(A). Asymptomatic and persistent SBP of ≥ 140 - <170 mmHg, or DBP ≥ 90 - <110 mmHg, or a clinically significant increase in DBP of 20 mmHg (but still below 110 mmHg).	Step 1. Continue pazopanib at the current dose. Step 2. Adjust current or initiate new antihypertensive medication(s). Step 3. Titrate antihypertensive medication(s) during next 2 weeks as indicated to achieve well-controlled ^a blood pressure (BP). If BP is not well-controlled within 2 weeks, consider referral to a specialist and go to scenario (B).
(B). Asymptomatic SBP ≥ 170 mmHg, or DBP ≥ 110 mmHg, or failure to achieve well-controlled BP within 2 weeks in scenario (A).	Step 1. Consider reducing or interrupting pazopanib, as clinically indicated. Step 2. Adjust current or initiate new antihypertensive medication. Step 3. Titrate antihypertensive medication(s) during next 2 weeks as indicated to achieve well-controlled BP. Step 4. Once BP is well-controlled, restart pazopanib dose-reduced by 200 mg if it was interrupted.
(C). Symptomatic hypertension or recurring SBP ≥ 170 mmHg, or DBP ≥ 110 mmHg, despite modification of antihypertensive medication(s)	Step 1. Interrupt pazopanib. Step 2. Adjust current or initiate new antihypertensive medication(s). Step 3. Titrate antihypertensive medication(s) during next 2 weeks as indicated to achieve well-controlled BP. Referral to a specialist for further evaluation and follow-up is also recommended. Step 4. Once BP is well-controlled, restart pazopanib dose-reduced by 200 mg.
(D). Refractory hypertension unresponsive to above interventions.	Discontinue pazopanib and continue follow-up per protocol.
Proteinuria	
UPC <3	Continue pazopanib at the current dose; monitor as clinically indicated
UPC ≥ 3 or 24-h urine protein ≥ 3 g	Step 1. Interrupt pazopanib. Step 2. Weekly UPC or 24-hr urine protein monitoring until UPC is <3 or 24-hr urine protein is <3 g. Then restart pazopanib dose-reduced by 200 mg. Step 3. If UPC ≥ 3 or 24-h urine protein ≥ 3 g recurs, repeat steps 1 and 2 Step 4. If UPC ≥ 3 or 24-hr urine protein ≥ 3 g recurs and the pazopanib dose can no longer be reduced, discontinue pazopanib and continue follow-up per protocol.

AE Terms & Descriptions	Dose Modification Algorithms
Hemorrhage/Bleeding: Investigate and document underlying etiology of the bleeding	
Grade 1	For hemoptysis, interrupt pazopanib and consider whether further treatment with pazopanib is appropriate. For other grade 1 hemorrhage/bleeding event, continue pazopanib at the current dose; monitor as clinically indicated.
Grade 2	Step 1. If pulmonary or GI bleed (other than hemorrhoidal bleeding), discontinue pazopanib and continue follow-up per protocol. Otherwise, interrupt pazopanib until the AE resolved to \leq grade 1. Step 2. Restart pazopanib; consider reducing dose and monitor as clinically indicated.
Grade 3 or 4, or recurrent \geq grade 2 event after dose interruption/reduction.	Discontinue pazopanib and continue with follow-up per protocol.
Venous Thrombosis (DVT, PE)	
Grade 2	Continue pazopanib at the current dose; monitor as clinically indicated
Grade 3	Step 1. Interrupt pazopanib. Step 2. Initiate and monitor anticoagulation as clinically indicated. Step 3. Resume pazopanib at reduced dose only if all of the following criteria are met: 
 • The subject must have been treated with anticoagulant at the desired level of anticoagulation for at least one week. • No grade 3 or 4 or clinically significant grade 2 hemorrhagic events have occurred while on anticoagulation treatment. Subject should be monitored as clinically indicated during anticoagulation treatment and after resuming study treatment. When treating with warfarin, international normalized ratio (INR) should be monitored within three to five days after any change in pazopanib dosing (e.g., re initiating, escalating/de-escalating, or discontinuing pazopanib), and then at least weekly until the INR is stable. The dose of warfarin (or its derivatives) may need to be adjusted to maintain the desired level of anticoagulation
Grade 4 and/or PE	Discontinue pazopanib and continue follow-up per protocol.
Arterial Thrombosis/Ischemia	
Any grade	Discontinue pazopanib and continue follow-up per protocol.
Thrombocytopenia: Investigate and document underlying cause	
Grade 1 or 2	Continue pazopanib with current dose; monitor as clinically indicated.
Grade 3 or 4	Step 1. Interrupt pazopanib until toxicity resolves to \leq grade 2. Step 2. Restart pazopanib dose-reduced by 200 mg and monitor as clinically indicated. If no recovery to \leq grade 2 or recurrent grade 3 or 4 thrombocytopenia, discontinue pazopanib and follow-up per protocol
Anemia: No specific dose reduction rules are indicated for anemia unless due to hemorrhage or bleeding as noted above.	
Palmar-plantar Erythrodysesthesia Syndrome	
Grade 1 Minimal skin changes or dermatitis without pain (erythema, edema,	Continue pazopanib with current dose.

AE Terms & Descriptions	Dose Modification Algorithms
hyperkeratosis)	
Grade 2 Skin changes with pain; limiting instrumental activities of daily living (peeling, blisters, edema, bleed, hyperkeratosis)	Step 1. Hold pazopanib. Step 2. Treat as clinically appropriate. Step 3. Upon resolution to grade 1 or better, restart pazopanib with a dose reduction to 400 mg. Step 4. If recurrent, consider a further dose reduction to 200 mg or discontinuation.
Grade 3 Severe skin changes with pain and limiting self-care activities of daily living	Discontinue pazopanib
Other Clinically Significant Adverse Events^b	
Grade 1	Continue pazopanib; monitor as clinically indicated.
Grade 2 or 3, if clinically significant	Step 1. Interrupt pazopanib until toxicity resolves to \leq Grade 1. Step 2. Restart pazopanib dose-reduced by 200 mg and monitor as clinically indicated.
Grade 4	Discontinue pazopanib and continue follow-up per protocol.
Prolongation of QTc Interval: If the QTc is prolonged, the ECG should be manually read to ensure accuracy of the reading. The values below refer to manually-read ECGs.	
QTc \geq 480-500 msec	Continue pazopanib; monitor as clinically indicated.
QTc \geq 500 msec	Discontinue pazopanib and continue follow-up per protocol.

a. Well-controlled BP defined as SBP <140 mmHg and mean DBP <90 mmHg.

b. AEs are graded according to NCI Common Terminology Criteria for Adverse Events v4.0 (NCI CTCAE v4)

Guidelines for Management of Treatment Emergent Hepatotoxicity

Event	Dose Modification Algorithms
(A). ALT of \leq 3.0 x ULN	Continue pazopanib at current dose with full panel LFTs ^a monitored as per protocol.
(B). ALT >3.0 x ULN to \leq 8.0 x ULN without bilirubin elevation (defined as total bilirubin ^b <2.0 x ULN or direct bilirubin \leq 35%) and without hypersensitivity symptoms (e.g., fever, rash)	Step 1. Continue pazopanib at current dose levels. Step 2. Monitor subject closely for clinical signs and symptoms; perform full panel LFTs ^a weekly or more frequently if clinically indicated until ALT is reduced to grade 1.
(C). ALT >8.0 x ULN without bilirubin elevation (defined as total bilirubin ^b <2.0 x ULN or direct bilirubin \leq 35%) and without hypersensitivity symptoms (e.g., fever, rash)	1st occurrence – Liver Event Interruption Criteria: Step 1. Interrupt pazopanib until toxicity resolves to \leq grade 1 or baseline. Report the event to Novartis as an SAE within 24 hours of learning of its occurrence. Make every reasonable attempt to have subjects return to the clinic within 24 to 72 hours for repeat liver chemistries and liver event follow up assessments. Step 2. Liver imaging and other laboratory investigations should be considered as clinically appropriate. Step 3. Monitor subject closely for clinical signs and symptoms; perform full panel LFTs ^a weekly or more frequently if clinically indicated until ALT is reduced to grade 1. Step 4. If the subject is benefiting from the study treatment, re-treatment may be considered if ALL following criteria are met: - ALT reduced to Grade 1

Event	Dose Modification Algorithms
	
 - Total bilirubin <1.5 x ULN or direct bilirubin ≤35% - No hypersensitivity signs or symptoms - Subject is benefiting from therapy. 
Recurrence – Liver Event Stopping Criteria: Discontinue pazopanib permanently and monitor subject closely for clinical signs and symptoms; perform full panel LFTs^a weekly or more frequently if clinically indicated until ALT is reduced to grade 1.

(D). ALT >3.0 x ULN with concomitant elevation in bilirubin^b (defined as total bilirubin ≥2.0 x ULN; with direct bilirubin >35%) or with hypersensitivity symptoms (e.g., fever, rash).
	
Liver Event Stopping Criteria: Step 1. Discontinue pazopanib immediately, report the event to Novartis as an SAE within 24 hours of learning of its occurrence. Make every reasonable attempt to have subjects return to the clinic within 24 hours for repeat liver chemistries and liver event follow up assessments. Step 2. Consult a gastroenterologist / hepatologist and perform the following assessments to identify potential co-factors:
 
 - Eosinophil count - Viral serology for hepatitis A, B, C and E, cytomegalovirus, Epstein-Barr virus (IgM antibody, heterophile antibody, or monospot testing) - Anti-nuclear antibody, anti-smooth muscle antibody, Type 1 anti-liver kidney microsomal antibodies. - Serum creatinine phosphokinase for possible muscle injury caused LFT elevation - Liver imaging - Consider toxicological blood screen for possible contributing chemical/medical entities 
Step 3. Monitor subject closely for clinical signs and symptoms; record the appearance or worsening of clinical symptoms of hepatitis, or hypersensitivity, such as fatigue, nausea, vomiting, right upper quadrant pain or tenderness, fever rash or eosinophilia as relevant on the AE report form. Perform full panel LFTs^a weekly or more frequently if clinically indicated until LFTs are reduced to grade 1.


For isolated total bilirubin^b elevation without concurrent ALT increases (defined as ALT < 3 X ULN).
	
Step 1. Isolated hyperbilirubinemia (i.e., in the absence of elevated ALT or other signs/symptoms of liver injury) does not require dose modification. Pazopanib inhibits UGT1A1 and OATP1B1, which can cause elevation of indirect (unconjugated) bilirubin in the absence of liver injury. Step 2. If bilirubin is >1.5 x ULN in the absence of ALT elevation, fractionation of bilirubin elevation should be performed. If bilirubin is >35% direct (conjugated), further evaluation for underlying cause of cholestasis should be performed.

Event	Dose Modification Algorithms
a. Full panel LFTs include: AST, ALT, alkaline phosphatase, and total bilirubin. Coagulation tests should be performed as clinically indicated. b. Serum bilirubin fractionation should be performed if testing is available. If testing is unavailable and a subject meets the criterion of total bilirubin >1.5 x ULN, then the event should be promptly reported as an SAE.	

Please see Section 7.8 for adverse event reporting instructions for hepatotoxicity.

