3.0 PATIENT SELECTION

3.1 Inclusion Criteria

1. Histologically confirmed diagnosis of advanced (metastatic or unresectable) non-small cell lung cancer (NSCLC) with mutations, rearrangement and fusion involving RET oncogene, or abnormalities in the pazopanib target genes defined as VEGFR1-3, PDGFRA, PDGFRB, or TP53 with abnormalities including deletion, insertion, early stop codon, and/or nonsynonymous mutations with functional consequences. CLIA certified lab testing for pazopanib target genes using cell free DNA from peripheral blood and/or assays performed on tumor tissues are acceptable.
2. Evaluable disease by imaging or physical exam OR measurable disease defined as at least one lesion that can be accurately measured in at least one dimension (longest diameter to be recorded) as ≥ 10 mm with CT scan, as ≥ 20 mm by chest x-ray, or ≥ 10 mm with calipers by clinical exam.
3. Failed at least one standard chemotherapeutic treatment for NSCLC.
4. At least 18 years of age.
5. ECOG performance status ≤ 2 (see Appendix A)
6. Normal bone marrow and organ function as defined below:
 - a. Absolute neutrophil count $\geq 1,500/\text{mcl}$
 - b. Platelets $\geq 100,000/\text{mcl}$
 - c. Hemoglobin ≥ 9.0 g/dL

- d. PT or INR $\leq 1.2 \times$ IULN
 - e. aPTT $\leq 1.2 \times$ IULN
 - f. Total bilirubin $\leq 1.5 \times$ IULN
 - g. AST(SGOT)/ALT(SGPT) $\leq 2.5 \times$ IULN
 - h. Creatinine ≤ 1.5 mg/dL OR creatinine clearance ≥ 30 mL/min/1.73 m² for patients with creatinine levels above 1.5 mg/dL
 - i. UPC < 1 or, if UPC ≥ 1 , 24-hour urine protein < 1 g; use of urine dipstick for renal function assessment is not acceptable.
7. Patients receiving anticoagulation therapy are eligible if their INR is stable and within the recommended range for the desired level of anticoagulation.
 8. Ability to swallow and retain oral tablets.
 9. Women of childbearing potential and men must agree to use adequate contraception (hormonal or barrier method of birth control, abstinence) prior to study entry and for the duration of study participation. Should a woman become pregnant or suspect she is pregnant while participating in this study, she must inform her treating physician immediately.
 10. Ability to understand and willingness to sign an IRB approved written informed consent document.

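### The proteinuria rows of Section 6.0 support opposing dose instructions when UPC and 24-hour urine protein disagree

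*Combined protocol and SAP*

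**What the plan says.** The proteinuria part of the dose modification table in Section 6.0 has two rows.

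- **Continue.** The first row is headed by UPC below 3 and says "Continue pazopanib at the current dose; monitor as clinically indicated". It does not mention 24-hour protein.
- **Interrupt.** The second row is entered on "UPC ≥ 3 or 24-h urine protein ≥ 3 g", and its Step 1 is to interrupt.
- **Monitor and restart.** Step 2 calls for "Weekly UPC or 24-hr urine protein monitoring" "until UPC is <3 or 24-hr urine protein is <3 g. Then restart pazopanib dose-reduced by 200 mg".
- **Recurrence.** Step 3 reads "If UPC ≥ 3 or 24-h urine protein ≥ 3 g recurs, repeat steps 1 and 2". Step 4 covers the case where the abnormality "recurs and the pazopanib dose can no longer be reduced, discontinue pazopanib and continue follow-up per protocol".

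The general rules at the start of Section 6.0 set the ladder at 800, 600, 400 and 200 mg, then discontinuation. They also allow re-escalation if the toxicity has abated and the investigator considers it safe.

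Two other places use these tests. Inclusion item 6i in Section 3.1 requires "UPC < 1 or, if UPC ≥ 1 , 24-hour urine protein < 1 g", so it states how they combine for eligibility. The study calendar in Section 10.0 schedules UPC at screening, on Day 1 of each cycle through Cycle 6, on Day 1 of even-numbered cycles after that, and at end of treatment. It does not list 24-hour protein.

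**The concern.** The interrupt trigger and the restart test both join the two measures with an or. The opposite of an either-test trigger is that both tests are below the limit, so an either-test restart overlaps the trigger instead of complementing it. The continue row is defined by UPC alone and the interrupt row by either test, so those two rows overlap as well.

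Interruption, a 200 mg reduction and permanent discontinuation all hang on this part of the table. Two investigators holding the same pair of results could act differently, each within the text: one keeps the patient on drug and the other interrupts, or one restarts and the other waits. This bears on patient safety. It also bears on drug exposure in a 20-patient single-arm study whose primary objectives are response rate and progression-free survival.

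**Working it through.** No figure in the plan needs reproducing here. The check sets each combination of results against the rules as written.

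**Inputs (Section 6.0, proteinuria rows)**

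- Continue: UPC < 3.
- Interrupt: UPC ≥ 3 or 24-hour protein ≥ 3 g.
- Restart, 200 mg lower: UPC < 3 or 24-hour protein < 3 g.

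**All combinations**

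| UPC | 24-hour protein | Continue met | Interrupt met | Restart met | Conflict |
|---|---|---|---|---|---|
| < 3 | < 3 g | yes | no | yes | none |
| ≥ 3 | ≥ 3 g | no | yes | no | none |
| ≥ 3 | < 3 g | no | yes | yes | interrupt and restart |
| < 3 | ≥ 3 g | yes | yes | yes | continue and interrupt; also interrupt and restart |

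Both discordant states conflict and neither concordant state does. If the restart test required both values to be below the limit, it would be met only in the first line, where the trigger is not, and the interrupt and restart overlap would vanish. The continue and interrupt overlap in the last line would remain, because it comes from the row definitions and not from Step 2.

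**One test throughout.** With UPC alone, the trigger is ≥ 3 and the restart is < 3, which are complements. The same holds for 24-hour protein alone at 3 g. A conflict needs both results in hand and disagreeing, or one test that triggers and the other that clears. Step 2 allows the second case, since it accepts either test during the interruption and does not tie the clearing test to the triggering one.

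**When discordance can occur (illustration only).** Assume that UPC is in g per g and reflects the 24-hour ratio. Then 24-hour protein (g) = UPC × daily creatinine excretion (g). The documents give no excretion figure, so take 0.7 to 1.5 g/day as an assumed range:

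- 0.7 g/day: 3 / 0.7 = 4.29, so a UPC from 3.0 to just under 4.29 goes with 24-hour protein from 2.1 g to just under 3 g (interrupt and restart).
- 1.0 g/day: the two values are equal and there is no discordance.
- 1.5 g/day: 3 / 1.5 = 2.0, so a UPC from 2.0 to just under 3.0 goes with 24-hour protein from 3.0 g to just under 4.5 g (continue and interrupt).

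This shows that discordant pairs are possible. It does not show how common they are, and the overlap in the table does not depend on it.

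**Dose ladder.** The first trigger, at 800 mg, leads to restart at 600. The second leads to 400 and the third to 200. A fourth, at 200, allows no further reduction, so the drug is discontinued. That is three reductions and a fourth trigger. The path requires one test to trigger and the other to clear on every round, with no re-escalation in between.

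**The case against.** The strongest reply is that Step 2 should be read in parallel: monitor by one test or the other, until that same test is below its limit. Restart is then the complement of the trigger for whichever test is in use. This is a plausible reading of Step 2, but the text does not state it. It also leaves the first row untouched, so UPC below 3 with 24-hour protein of 3 g or more still meets continue and interrupt.

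Second, discordant pairs are not part of the routine schedule. The calendar lists only UPC, and nothing requires a 24-hour collection when UPC is below 3. This stands and limits how often the problem can arise. It does not remove the problem, because the table itself names both tests.

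Third, the steps are sequential. The restart test applies to monitoring results after the interruption, so it is not a second instruction on the result that triggered it. This stands.

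Three stronger readings are tempting, and the documents do not support them:

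- **Automatic step-down.** A reader might infer that a patient with a stable UPC of 3.5 and 24-hour protein of 2.5 g must descend to discontinuation. Under weekly UPC alone, 3.5 never meets the restart test, so that patient stays interrupted and does not move down the ladder. Weekly testing is specified only for the interruption; after restart, scheduled UPC follows the calendar. Steps 3 and 4 require recurrence, and a value that never cleared has arguably persisted. Re-escalation is also allowed.
- **Contradiction with eligibility.** A reader might infer that Section 6.0 contradicts inclusion item 6i. Eligibility and on-treatment management serve different purposes and use different limits (1 and 3), so treating the tests differently is not in itself an inconsistency. Item 6i shows only that the protocol can state how the tests combine.
- **Distorted efficacy results.** A reader might infer a material effect on the response or progression-free survival estimates. Without a frequency of discordance this cannot be sized, and the planned analysis is descriptive.

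**Conclusion.** The point holds as a self-conflicting dosing rule. The continue, interrupt and restart conditions for proteinuria are not mutually exclusive, and both discordant combinations, two of the four, support opposing instructions. The clash between the continue and interrupt rows is the firmest part, because no reading of Step 2 removes it. The clash between interrupt and restart depends on Step 2 being taken as written and not as one test followed throughout.

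The practical size is unknown. The conflict does not reach a patient followed by a single test, only UPC is scheduled, and the documents do not allow an estimate of how many of the 20 patients would have discordant results. Repeated reductions ending in discontinuation are possible only on the path described above. The conclusion rests on the wording of the rows and not on the assumed creatinine range. It is worth correcting because the rule governs interruption and discontinuation and the correction is cheap.

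**What to change.** The sponsor should reconcile the continue, interrupt, restart and recurrence wording in the proteinuria rows so that:

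1. each pair of UPC and 24-hour results falls under exactly one instruction, including the case where only one test has been done;
2. the restart condition is the complement of the interrupt condition;
3. recurrence is defined in the same terms, including whether a value that never cleared on its own test counts.

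How the two tests combine, and whether the test that triggered an interruption must also be the one that clears it, is for the sponsor to decide. A four-line table like the one above, completed for the new wording, would confirm that no combination has two instructions or none.

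The cost is a wording amendment to one part of the Section 6.0 table. If the chosen rule makes the 24-hour value necessary, it also requires those collections and an entry in the Section 10.0 calendar; otherwise no test is added.

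### Two dose rules in Section 6.0 fail at specific patient states: a QTc of exactly 500 msec meets opposite instructions, and the fixed 400 mg hand-foot restart is not a reduction at 400 or 200 mg (minor; wording fix)

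*Combined protocol and SAP*

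**What the plan says.** All the rules at issue are in Section 6.0, Dose Delays/Dose Modifications.

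- **QTc.** There are two rows. For 480 to 500 msec, pazopanib continues with monitoring as clinically indicated. For 500 msec or more, pazopanib is discontinued. The lead-in adds: "The values below refer to manually-read ECGs".
- **Hand-foot syndrome, grade 2.** The drug is held and the event treated. Step 3 is "Upon resolution to grade 1 or better, restart pazopanib with a dose reduction to 400 mg". Step 4 is "If recurrent, consider a further dose reduction to 200 mg or discontinuation".
- **General rule.** When a reduction is needed, "the dose should be reduced stepwise by 200 mg at each step". The dose-level table runs 800, 600, 400, 200 mg, then Discontinue (level -4).
- **Re-escalation.** If toxicity has abated and the investigator considers it safe, "the pazopanib dose can then be increased step-wise back to the pre-event dose".
- **At 200 mg.** "For patients at dose-level -3, 200 mg QD, a maximum dose delay of 14 days is allowed for management of toxicities", and "If toxicity does not resolve in 14 days, the patient should be discontinued from study".
- **Other clinically significant events, grade 2 or 3.** After resolution: "Restart pazopanib dose-reduced by 200 mg and monitor as clinically indicated".

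**The concern.** A dose-modification table should give one instruction for each state a patient can be in. These two rules do not.

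At a QTc of exactly 500 msec, one row allows dosing to go on and the next stops it permanently. The requirement for a manual reading settles what the value is; it does not say which row applies.

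The hand-foot row names a target dose, where most other rows name a step. A fixed target is a reduction only for patients above it. A first grade 2 hand-foot event in a patient already at 400 mg is a reachable state: the rows for hypertension (scenarios B and C), proteinuria, thrombocytopenia and other events each provide a 200 mg reduction, so two such reductions put a patient at 400 mg. Read by its number, Step 3 then restarts that patient at the dose at which the event occurred. Three earlier reductions put a patient at 200 mg, where the number in Step 3 cannot sensibly be used.

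What is at stake is a clear default for the site in a few uncommon states.

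**Working it through.** The plan states no figure on this point to reproduce. The check applies each rule, as written, to each possible state.

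**QTc.** Inputs are the two rows in Section 6.0. Continue applies if 480 ≤ QTc ≤ 500; discontinue applies if QTc ≥ 500.

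| QTc (msec) | Continue row | Discontinue row | Continue row if it ended below 500 |
|---|---|---|---|
| 479 | no | no | no |
| 480 | yes | no | yes |
| 490 | yes | no | yes |
| 499 | yes | no | yes |
| 500 | **yes** | **yes** | no |
| 501 | no | yes | no |

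The rows overlap at one point, 500 msec. With an exclusive upper bound on the continue row the overlap disappears and no value from 480 upward is left uncovered.

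Other numeric rows in Section 6.0 keep their bounds apart. Systolic pressure in hypertension scenario A stops below 170 mmHg and scenario B starts at 170; UPC is split at below 3 versus 3 or more; ALT is split at up to 8.0 versus above 8.0 times ULN.

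**Hand-foot syndrome, grade 2, first event.** Inputs are the dose levels (800, 600, 400, 200 mg), the Step 3 target (400 mg) and the general step (200 mg). Change under Step 3 = 400 − dose at onset. Dose under the general rule = dose at onset − 200.

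| Dose at onset (mg) | Change under Step 3 (mg) | General rule and dose-level table |
|---|---|---|
| 800 | 400 − 800 = −400 | 600 mg |
| 600 | 400 − 600 = −200 | 400 mg |
| 400 | 400 − 400 = **0** | 200 mg |
| 200 | 400 − 200 = **+200** | Discontinue (level -4) |

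At 400 mg the number in Step 3 contradicts the step's own description of itself as a reduction. At 200 mg it would exceed the dose before the event, which is the ceiling Section 6.0 sets for re-escalation.

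**What else in Section 6.0 could settle these states?**

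- Step 4 names 200 mg, but only for a recurrence, and only as something to consider.
- The general step rule would give 200 mg from 400 mg. It is offered as a general rule, and the hand-foot row already departs from it at 800 mg (−400 rather than −200). Nothing says when the row gives way to it.
- At 200 mg, the 14-day limit requires stopping if the toxicity has not resolved in time. A restart at 200 mg after earlier resolution is implied, not stated, while the dose-level table places discontinuation below 200 mg.

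**The case against.** The strongest reply is that a sensible investigator would not go wrong. Step 3 asks for a reduction as well as naming 400 mg, so restarting a 400 mg patient at 400 mg does not satisfy the sentence; the general rule and the dose-level table supply 200 mg, and discontinuation below that. For QTc, the hypertension row shows the intended style (an explicit less-than sign on the upper bound), and the stop row at 500 msec is unambiguous. A less-than sign could have been lost in drafting or in reading the PDF. Section 5.4 lets the investigator stop the drug for an adverse event, and Section 6.0 allows interruption or a further decrease if toxicity does not abate.

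Much of this stands, and it is why the point is minor. It does not remove the defect. The sensible answer has to be inferred against a number printed in the row. Less-than signs survive elsewhere in the same table, so a lost sign in this one row is possible but is not the natural reading.

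A reader might infer more than the documents support:

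- *That the protocol orders a dose increase at 200 mg, or forces unsafe dosing.* It does not. Step 3 calls the restart a reduction, re-escalation is capped at the dose before the event, and the investigator may stop or reduce.
- *That the hand-foot row is wrong because it differs from the row for other events.* A toxicity-specific row may be stricter or milder. The fault is the internal contradiction at 400 mg and the absence of a usable instruction at 200 mg.

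**Conclusion.** Both defects are present in the text as written, and both are minor. The QTc conflict is confined to one value, 500 msec. The hand-foot restart fails for a first grade 2 event at 400 mg (no reduction) and at 200 mg (named dose above the current one); it works at 800 and 600 mg, and 800 mg is the starting dose.

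The documents give no rates from which to predict how many of the 20 patients would reach these states. That they will be few is a judgement: it takes a QTc exactly at the boundary, or at least two earlier reductions without re-escalation followed by a first grade 2 hand-foot event.

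A reader might also infer that the efficacy results are compromised. The documents do not support that: the sample size, the response-rate estimate and the PFS analysis do not depend on these rows. The conclusion assumes that the QTc row is printed in the original as it reads here.

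**What to change.** Change the wording in three places in Section 6.0.

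1. **QTc, continue row:** ≥480 to <500 msec. Leave discontinuation at ≥500 msec.
2. **Hand-foot grade 2, Step 3:** once the event is back to grade 1 or less, restart at 400 mg if the dose at onset was 600 or 800 mg, or at 200 mg if it was 400 mg; if it was 200 mg, discontinue (dose level -4). If the sponsor prefers to allow a restart at 200 mg when the event resolves within 14 days, Step 3 should say so explicitly; that is a clinical choice.
3. **Hand-foot grade 2, Step 4:** keep it for a recurrence at any dose and add only that a recurrence at 200 mg leads to discontinuation. It should not be narrowed to recurrence at 400 or 200 mg, because re-escalation is permitted and a patient could recur at 600 or 800 mg.

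The cost is a few lines in one amendment, with no added visits, tests or data.
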